4.6.1.9 Vital Signs

Vital signs will include resting blood pressure (BP), heart rate, respiratory rate and body temperature and will be recorded at the visits specified in the Schedule of Assessments ([Appendix 1](#)).

Blood pressure, heart rate and respiratory rate should be obtained in a quiet room at a comfortable temperature, with the patient's arm unconstrained by clothing or other material. All measurements will be obtained from the same arm and, with the same cuff size, using a well-calibrated automatic instrument with a digital readout, throughout the study (the "ideal" cuff should have a bladder length that is 80% and a width that is at least 40% of arm circumference [a length-to-width ratio of 2:1]). The automatic cuff should be placed on the designated arm prior to the patient being in a resting position. The patient should be asked to remove all clothing that covers the location of cuff placement. The individual should be comfortably seated, with the legs uncrossed, and the back and arm supported, such that the middle of the cuff on the upper arm is at the level of the right atrium (the mid-point of the sternum). After the patient has been resting in semi-recumbent position for ≥ 10 minutes, blood pressure, heart rate and respiratory rate will be obtained.

4.6.1.10 Administering the SF36 and ESSPRI (Patient-Reported Outcomes)

The SF36 & ESSPRI are PRO instruments which will be completed by patients in this study to more fully characterize the clinical profile of RO5459072. The PRO instruments, translated as required in the local language, will be distributed in paper PRO booklet format by the Investigator staff and completed in their entirety by the patient at specified visits during the study.

Entries should be reviewed for completeness by the site staff during the visit and the patient/caregiver should be requested to complete any blank items. Changes to the form should not be made once the patient/caregiver has left the site for that visit.

The paper PRO booklets are part of the source documentation. A visit-specific paper PRO booklet, containing the PRO assessments for that study day, will be provided. Patients should complete the PRO booklets at the beginning of each study visit, prior to other study assessments or discussion of health status.

4.6.1.11 MSG Biopsies (Optional Sub-study)

At selected participating study centers, patients may also enroll into an optional sub-study in which consenting individuals will undergo labial (MSG) biopsies for assessing histological and structural changes in labial salivary glands using, e.g., immunohistochemistry.

Biopsies will be taken using a minimally invasive technique according to standard practice at each study center, e.g., multiple 2-3mm incisions on the buccal side of the lip

to collect the glandular tissue using forceps. Biopsy sample handling and shipment instructions will be provided in a separate laboratory manual. Histology and immunohistochemistry methods will be described and reported separately.

4.6.1.12 Timing of Assessments - Screening and Pretreatment Assessments

Written informed consent for participation in the study must be obtained before performing any study-specific screening tests or evaluations. Informed Consent Forms for enrolled patient and for patients who are not subsequently enrolled will be maintained at the study site.

All screening and pre-treatment assessments must be completed and reviewed to confirm that patients meet all eligibility criteria. The Investigator will maintain a screening log to record details of all patients screened and to confirm eligibility or record reasons for screening failure. Based on the Investigator judgment, patients may be re-screened and enrolled if the patient meets all of the eligibility criteria at a later time-point.

An Eligibility Screening Form (ESF) documenting the Investigator's assessment of each screened patient with regard to the protocol's inclusion and exclusion criteria is to be completed by the Investigator and kept at the investigational site.

Screening and pre-treatment assessments will be performed within 28 days prior to first dose of study drug treatment, unless otherwise specified. After the study completion/early termination visit, adverse events should be followed as outlined in Sections [5.5](#), [5.4.3](#) and [5.6](#).

For assessments, and timing of assessments, please see the SoA table ([Appendix 1](#)).

4.7 PATIENT, STUDY, AND SITE DISCONTINUATION

4.7.1 Patient Discontinuation

The Investigator has the right to discontinue a patient from RO5459072 or withdraw a patient from the study at any time. In addition, patients have the right to voluntarily discontinue study drug or withdraw from the study at any time for any reason. Reasons for discontinuation of study drug or withdrawal from the study may include, but are not limited to, the following:

- Patient withdrawal of consent at any time.
- Pregnancy.
- Any medical condition that the Investigator or Sponsor determines may jeopardize the patient's safety if he or she continues in the study.
- Investigator or Sponsor determines it is in the best interest of the patient.
- The patient requires corticosteroid therapy exceeding 7.5 mg prednisone equivalent per day, or the dose of existing corticosteroid therapy is increased during the study

treatment period (see Section 4.5.2 and Appendix 3), or institution of any other immunosuppressive therapy, or an increase in dose of existing therapy.

Every effort should be made to obtain information on patients who withdraw from the study. The primary reason for withdrawal from the study should be documented on the appropriate eCRF.

Patients will not be followed for any reason after consent has been withdrawn. Patients who withdraw from the study will not be replaced.

Under no circumstances will patients who enroll in this study and have completed treatment as specified, be permitted to be allocated a new randomization number and re-enroll in the study.

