3. STUDY DESIGN

3.1 DESCRIPTION OF STUDY

3.1.1 Overview of Study Design

[figure not shown]
Study BP30037 is a randomized, double-blind, placebo-controlled, two-treatment arm, parallel-group study designed to evaluate the effects of RO5459072 treatment on disease activity and symptoms of Sjögren's syndrome in adult patients with moderate to severe primary Sjögren's syndrome. Patients will be randomized 1:1 to receive either 100 mg RO5459072 or placebo orally twice daily (b.i.d.) and will be treated for a maximum of 12 weeks. Based on the Investigator judgment, patients may be re-screened and enrolled if the patient meets all of the eligibility criteria at a later time-point.

Assessments of Sjögren's syndrome disease activity, symptoms and quality of life will be made before (baseline [Week -1]), during the study treatment phase, upon completion and, at the early termination visit and at the safety and follow-up visit in order to evaluate the efficacy of RO5459072 treatment. Patients will start study drug treatment one day after the *last* baseline *assessment*. In addition, patients will undergo pharmacodynamic assessments of exocrine gland function and provide samples for measurement of white blood cell numbers and levels of biomarkers associated with Sjögren's syndrome or connected to the mechanism of action of RO5459072, as well as RO5459072 plasma concentrations. Safety and tolerability will be assessed throughout the study.

At selected participating study centers, patients may also enroll into an optional sub-study in which consenting individuals will undergo minor salivary gland (MSG) biopsies for assessing histological changes in labial salivary glands. Biopsies will be taken at baseline (Week -1) and at the end of the study drug treatment period (Week 12, ± 1 week). The data from the sub-study will be analyzed and reported separately.

Patients may concomitantly receive standard of care symptomatic treatment (see Section [4.5.1](#)).

Figure 3 Study Design

The total duration of the study for each patient will be (up to) 18 weeks:

- Screening visit: Up to 28 days prior to 1st dose.
- Baseline visit (BL): Up to 7 days prior to 1st dose.
- Treatment period: Up to 12 weeks (Days 1 to 84).
- Follow-up visit: 14 days after last dose.

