3.3.5 Exploratory Outcome Measures

The exploratory outcomes for this study are as follows:

- Comparisons of the performance of alternative composite endpoints (e.g., Sjögren's response index [SSRI-30]) as predictive markers of drug treatment response.
- Change from Week 12 to follow-up for ESSDAI, ESSPRI and SF-36 scores in each treatment group.
- Comparisons of drug treatment effects between genotypes.
- Patterns of use of selected concomitant medications.

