Appendix 1 Schedule of Assessments

Visit ⁸	Screening	Baseline ¹	Treatment Period				Follow-Up Visit	Early Termination Visit
			Week 2	Week 6	Week 9	Week 12		
Days	-28 to -8	-7 to -1	14 (± 7)	42 (± 7)	63 (± 7)	84 (± 7)	98 (± 7)	(NA)
Informed Consent	x							
Randomization		x						
Study drug dispensing		x	x	x				
Study drug return				x		x		x
Entry criteria	x	x						
Demography	x							
Medical History	x							
Physical Examination ²	x						x	x
Pregnancy testing ³	x	x	x	x	x	x	x	x
Tuberculosis testing	x							
HIV, HBV and HCV testing	x							
Clinical Genotyping		x						
ESSDAI score	x	x		x		x	x	x
ESSPRI score	x	x	x	x	x	x	x	x
SF-36		x		x		x		
Salivary samples ⁴		x	x	x		x		
Saliva flow assessment		x	x	x		x		
Tear samples ⁴		x	x	x		x		
Tear flow assessment		x	x	x		x		
mRNA sample		x	x	x		x		
Autoantibodies	x	x		x		x	x ⁵	x ⁵
Soluble biomarkers		x	x	x		x		
Immunophenotyping		x	x	x		x		
Cathepsin S activity/ mass		x	x	x		x		
ESR test		x	x	x		x		
PK sample			x	x		x		
Safety laboratory assessments ⁶	x	x	x	x	x	x	x	x
ECG - 12 Lead	x	x	x	x	x	x	x	x
Vital Signs	x	x	x	x	x	x	x	x
MSG biopsy (optional sub-study only)		x				x ⁷		
Adverse Event or Intercurrent Illness	x							
Previous and Concomitant Treatments								

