Appendix 1 Schedule of Assessments (cont.)

1	First study drug administration should be one day after the last baseline assessment.
2	Physical examination includes weight, heart and respiratory rate, and body temperature.
3	All women will have serum pregnancy tests performed at screening and baseline. A urine pregnancy test will also be done at baseline prior to randomization. All women of childbearing potential will have serum and urine pregnancy tests at each subsequent visit.
4	The same salivary or tear sample is used for volume and biomarker assessments (see Section 4.6.1.3.4.).
5	Only markers required for ESSDAI scoring will be collected.
6	Safety laboratory assessment consists of hematology, blood chemistry, coagulation, lipids and urinalysis.
7	MSG biopsies procedures for the optional substudy may be performed at separate study center visits providing the procedures are carried out within the windows specified for the main study.
8	Screening, baseline and on-treatment visit schedules are all relative to the first day of study drug administration (Day 1). The follow-up visit is scheduled relative to the Week 12 end-of-treatment visit (+14 days after the end-of-treatment visit [\pm 7 days]).

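### Appendix 1 omits SF-36 at visits where the protocol calls for it, and its follow-up date conflicts with the last-dose rule for patients who stop drug early

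*Combined protocol and SAP*

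**What the plan says.** **SF-36.** Section 3.3.5, repeated in the synopsis under exploratory outcome measures, lists "Change from Week 12 to follow-up for ESSDAI, ESSPRI and SF-36 scores in each treatment group". Section 3.1.1 says that disease activity, symptoms and quality of life are assessed before and during treatment, on completion, and "at the early termination visit and at the safety and follow-up visit in order to evaluate the efficacy" of the drug. Two other places are narrower. The synopsis description of the study mentions only before, during and on completion of treatment, and Section 4.6.1.3.3 limits SF-36 to baseline and on-treatment visits. The SF-36 row of Appendix 1 marks baseline, Week 6 and Week 12, with nothing under follow-up or Early Termination.

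**Follow-up date.** The synopsis (length of study) and Section 3.1.1 put the follow-up visit two weeks after the last dose. Footnote 8 of Appendix 1 says instead: "The follow-up visit is scheduled relative to the Week 12 end-of-treatment visit", at 14 days with a window of 7 days either side.

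**Stopping drug.** Section 4.7.1 treats stopping drug and leaving the study as separate acts: "The Investigator has the right to discontinue a patient from RO5459072 or withdraw a patient from the study at any time". It gives patients the same two choices. Follow-up is ruled out only on loss of consent: "Patients will not be followed for any reason after consent has been withdrawn". For those who leave the study, "Every effort should be made to obtain information on patients who withdraw from the study". Appendix 1 has a column headed "Early Termination Visit" with drug return, ESSDAI, ESSPRI and safety tests, but no day is set for it. Section 4.6.1.12 mentions that visit together with study completion: "After the study completion/early termination visit, adverse events should be followed".

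**The concern.** A site works from the schedule of assessments. If SF-36 is not in the follow-up column it will not be collected, and a listed outcome loses one of its three instruments in every patient, completers included. No later analysis plan can recover it.

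The follow-up date matters because Section 3.2.5 gives the purpose of efficacy assessment at that visit as exploring acute rebound after treatment stops. Section 1.4.2 expects cathepsin S expression to normalise soon after stopping, and any pharmacodynamic rebound to be transient. A visit tied to Week 12 can fall long after an early stopper's last dose.

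The lesser matter is that no text says whether a patient who stops drug but keeps consent attends the remaining efficacy visits. Week 12 values not collected from such patients cannot be obtained later for a supportive analysis.

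**Working it through.** **1. SF-36: the texts side by side**

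| Place | SF-36 or quality of life at follow-up? | At Early Termination? |
|---|---|---|
| Section 3.3.5 and synopsis, exploratory outcomes | Required (change from Week 12) | Not addressed |
| Section 3.1.1 | Yes | Yes |
| Synopsis, description of study | Not mentioned | Not mentioned |
| Section 4.6.1.3.3 | No (baseline and on-treatment only) | No |
| Appendix 1 | No | No |

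The outcome is the follow-up score minus the Week 12 score. Appendix 1 supplies the second term but never the first, so the number of patients with a computable SF-36 change is 0 of 70. ESSDAI and ESSPRI are both scheduled at Week 12 and at follow-up, so those two parts of the outcome are unaffected.

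**2. Follow-up date**

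The plan's own figures reproduce for completers. Treatment runs from Day 1 to Day 84, and 84 + 14 = Day 98, the day printed in Appendix 1. Up to 28 days of screening + 84 + 14 = 126 days = 18 weeks, the stated duration.

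For a last dose on Day L, the design text gives L + 14. Footnote 8 gives nominal Day 84 + 14 = 98 whatever L is.

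| Last dose | Last dose + 14 | Footnote 8 (nominal) | Difference | Days off drug at footnote 8 date |
|---|---|---|---|---|
| Day 14 | Day 28 | Day 98 | 70 | 84 |
| Day 42 | Day 56 | Day 98 | 42 | 56 |
| Day 63 | Day 77 | Day 98 | 21 | 35 |
| Day 84 | Day 98 | Day 98 | 0 | 14 |

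If an early stopper never attends Week 12, footnote 8 has no visit to count from. Section 5.3.1 closes general adverse-event reporting 28 days after last dose. For a last dose on Day 14 that is Day 42, and 98 − 42 = 56 days before the footnote 8 date.

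**3. Visits after stopping drug**

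No arithmetic from the documents applies. The effort to obtain information in Section 4.7.1 concerns patients who leave the study and names no visit. The contents of the Early Termination column, and its pairing with study completion in Section 4.6.1.12, imply an exit visit. No text states what triggers it, or whether Weeks 6, 9 and 12 still apply to a patient who stays in the study off drug.

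**The case against.** **The schedule may be what the sponsor intends for SF-36.** The synopsis description and Section 4.6.1.3.3 agree with it. The rebound objective in Section 2.3 concerns disease activity and symptoms, which ESSDAI and ESSPRI cover at follow-up. The sentence in Section 3.1.1 could be a collective list, not a promise of every instrument at every visit. This stands as a reason to allow either correction. It does not remove the conflict, because Section 3.3.5 and the synopsis name SF-36 explicitly.

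**Footnote 8 may cover only patients who reach Week 12.** A patient who exits at Early Termination has no Week 12 visit, so the last-dose rule would govern. That reading is possible and would remove the 70- and 42-day gaps. But the footnote states no such limit, and the follow-up column prints Day 98 for everyone. Figure 3 might have helped but is not shown.

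**There is an implied path for stoppers.** The Early Termination visit collects drug returns, ESSDAI, ESSPRI and safety tests. Asking for later off-drug visits moves towards an effect regardless of stopping, which is a design choice in a phase 2a study. This stands, and it is why the third item is only optional.

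**A stronger reading is tempting: that missing off-drug visits bias the results.** One can assume that 5% to 15% of active-arm patients stop, with Week 12 ESSDAI changes 3 points worse than the model implies. The mixed-model difference would then be overstated by 0.05 × 3 = 0.15 to 0.15 × 3 = 0.45 points, against a standard error of 5 × √(2/35) = 1.195. The documents do not support the inference. They give no main-study stopping rate (the 15% in Section 6.1 is for the biopsy sub-study) and no outcome for stoppers. The shift is zero if both arms behave alike. It is also measured against an effect regardless of stopping, which the plan does not state as its target; Section 6.6.2 can be read as using on-treatment data only. The primary analysis is defined whatever happens, since Section 6.6.1 counts missing Week 12 data as non-response.

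**Conclusion.** Two inconsistencies are established and one omission is worth noting. All are minor.

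- **SF-36:** the Week 12 to follow-up change cannot be computed for any patient from the schedule as written. This needs no assumption. The loss is one component of one exploratory outcome, together with the quality-of-life assessment that Section 3.1.1 places at Early Termination.
- **Follow-up date:** the rules agree for completers (Day 98). For early stoppers footnote 8 either has no anchor visit or gives a later date, 70 days later for a last dose on Day 14. That this is too late for rebound rests on the protocol's own expectation that rebound is transient; the documents give no duration.
- **Visits after stopping drug:** the text is silent, with an exit path implied. Clarifying it is an optional improvement.

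A reader might infer a bias in the primary or mixed-model results. None is established, and no gain in power is claimed.

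**What to change.** 1. **SF-36.** Add it to the follow-up and Early Termination columns of Appendix 1, and bring Section 4.6.1.3.3 into line. Paper booklets with ESSPRI are already completed at both visits, so the cost is one more short questionnaire at follow-up per patient (at most 70) and one at each Early Termination visit. If the sponsor does not want it there, delete SF-36 from the outcome in Section 3.3.5 and the synopsis, and correct Section 3.1.1.
2. **Footnote 8.** Set follow-up at 14 days (± 7) after last dose, and limit the Week 12 to follow-up outcome to patients treated through Week 12. This is a wording change only.
3. **Optional.** In Section 4.7.1, say which visits follow drug stop when consent is kept. The sponsor may ask for an Early Termination visit at drug stop, follow-up 14 days after last dose, then the remaining ESSDAI, ESSPRI and SF-36 visits through Week 12. Visits with overlapping windows can be combined: for a last dose on Day 42, follow-up (Days 49 to 63) overlaps Week 9 (Days 56 to 70). Use the off-drug values only in one supportive analysis regardless of drug stopping. Because collecting them makes Week 12 non-missing, add a sentence keeping them out of the primary analysis, and keep patients who stopped for rescue corticosteroid or immunosuppressant as non-responders there. Otherwise a rescued patient could count as a responder. The cost is at most four already-designed visits per stopper (Weeks 2, 6, 9 and 12). At an assumed stopping rate of 5% to 15% that is about 4 to 10 patients (0.05 × 70 = 3.5; 0.15 × 70 = 10.5), some of whom will decline.

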4.7.2 Study and Site Discontinuation

The Sponsor has the right to terminate this study at any time. Reasons for terminating the study may include, but are not limited to, the following:

- The incidence or severity of adverse events in this or other studies indicates a potential health hazard to patients.
- Patient enrollment is unsatisfactory.

The Sponsor will notify the investigator and Health Authorities if the study is placed on hold, or if the Sponsor decides to discontinue the study or development program.

The Sponsor has the right to replace a site at any time. Reasons for replacing a site may include, but are not limited to, the following:

- Excessively slow recruitment.
- Poor protocol adherence.
- Inaccurate or incomplete data recording.
- Non-compliance with the International Conference on Harmonisation (ICH) guideline for Good Clinical Practice.

5. ASSESSMENT OF SAFETY

5.1 SAFETY PARAMETERS AND DEFINITIONS

Safety assessments will consist of monitoring and recording adverse events, including serious adverse events and non-serious adverse events of special interest; measurement of protocol-specified safety laboratory assessments; measurement of protocol-specified vital signs, ECGs; and other protocol-specified tests that are deemed critical to the safety evaluation of the study.

Certain types of events require immediate reporting to the Sponsor, as outlined in Section 5.4

5.1.1 Adverse Events

According to the ICH guideline for Good Clinical Practice, an adverse event is any untoward medical occurrence in a clinical investigation subject administered a pharmaceutical product, regardless of causal attribution. An adverse event can therefore be any of the following:

- Any unfavorable and unintended sign (including an abnormal laboratory finding), symptom, or disease temporally associated with the use of a medicinal product, whether or not considered related to the medicinal product.
- Any new disease or exacerbation of an existing disease (a worsening in the character, frequency, or severity of a known condition).
- Recurrence of an intermittent medical condition (e.g., headache) not present at baseline.
- Any deterioration in a laboratory value or other clinical test (e.g., ECG, X-ray) that is associated with symptoms or leads to a change in study treatment or concomitant treatment or discontinuation from study drug.
- Adverse events that are related to a protocol-mandated intervention, including those that occur prior to assignment of study treatment (e.g., screening invasive procedures such as biopsies).

5.1.2 Serious Adverse Events (Immediately Reportable to the Sponsor)

A serious adverse event is any adverse event that meets any of the following criteria:

- Fatal (i.e., the adverse event actually causes or leads to death).
- Life-threatening (i.e., the adverse event, in the view of the Investigator, places the patient at immediate risk of death).

This does not include any adverse event that had it occurred in a more severe form or was allowed to continue might have caused death.

- Requires or prolongs in-patient hospitalization (see Section [5.3.5.9](#)).
- Results in persistent or significant disability/incapacity (i.e., the adverse event results in substantial disruption of the patient's ability to conduct normal life functions).
- Congenital anomaly/birth defect in a neonate/infant born to a mother exposed to study drug.
- Significant medical event in the Investigator's judgment (e.g., may jeopardize the patient or may require medical/surgical intervention to prevent one of the outcomes listed above).

The terms "severe" and "serious" are not synonymous. Severity refers to the intensity of an adverse event (rated as mild, moderate, or severe, see Section [5.3.3](#)); the event itself

may be of relatively minor medical significance (such as severe headache without any further findings).

Severity and seriousness need to be independently assessed for each adverse event recorded on the eCRF.

Serious adverse events are required to be reported by the investigator to the Sponsor immediately (i.e., no more than 24 hours after learning of the event; see Section 5.4.2 for reporting instructions).

